#### 1) Four-week randomised, AB/BA crossover trial

Participants will be randomly allocated (1:1 ratio) to one of two sequences:

- Group 1: ALD-Aided (2 weeks), followed by usual care (non-ALD-Aided)
   (2 weeks); or
- o Group 2: Non-ALD-Aided (2 weeks), followed by ALD-Aided (2 weeks)

#### 2) Follow-on observational trial extension over 20 weeks

All participants will use the ALD for a period of 20 weeks following the end of the crossover period.

This means that the trial duration per participant will be 24 weeks in total.

It is anticipated that a minimum of 24 patients with mitochondrial disease and self-reported hearing loss will be screened in order to recruit 12 eligible participants (based on our previous findings as well as published studies reporting hearing loss and auditory processing deficits in patients with mitochondrial disease). Accounting for ~10% attrition (if two participants withdraw from the trial), this will allow for the trial to be completed by ten participants.

In total, participants will attend for four visits:

- Screening / Baseline, to be completed on the same day (at both Newcastle University and NE1Hear)
- Week 2 (NE1Hear)
- Week 4 (NE1Hear)
- Week 24 (NE1Hear and Newcastle Hospitals)

# TRIAL DEVICE

The device being utilised in this trial is the Phonak Roger On™ remote microphone. The Roger On™ is developed and manufactured by Phonak (a Sonova Company) https://www.phonak.com/uk/en/about-us.html.

Phonak have agreed to donate the devices to the Wellcome Centre for Mitochondrial Research, Newcastle University. The devices will be provided to participants for the duration of the trial.

This trial will be classed as a non-commercial trial of a UKCA/CE UKNI/CE marked device for a labelled indication, involving a change to standard care or randomisation between groups.

As it is taking place at a single site in England, MHRA notification of no objection is not required.

# **ELIGIBILITY CRITERIA**

Eligibility must be assessed by a suitably qualified and delegated member of the trial team (either a medically qualified doctor or appropriately experienced research team member e.g., research nurse, physiotherapist, exercise physiologist), and this assessment documented in the participant's medical records.

Only personnel formally delegated by the PI may assess eligibility.

#### **Inclusion Criteria**

To be eligible to participate all participants must:

- Be between 16 years and 70 years (aged ≥16 to ≤ 70 years)
- Have ability, in the opinion of the trial team, to participate in trial activities
- Be capable of providing informed consent
- Have a genetically confirmed diagnosis of mitochondrial disease
- Have confirmed hearing loss- via NMDAS hearing score of: 2 (mild), 3 (moderate), or 4 (severe)
- Have an NMDAS speech score of: 0 (normal), 1 (communication unaffected),
   or 2 (mild communication difficulties).
- Have evidence of impaired speech perception in background noise due to:
  - Significant sound detection defect measured by a 4-frequency average hearing detection threshold level (pure-tone-audiometry, ≥60 dBHL in the poorer ear) and/or
  - Impaired auditory processing (≤2 SDs from the normative mean)
     assessed by the 'Speech Reception Threshold' subtest of the Listening
     in Specialised Noise-Sentences (LiSN-S) test most reflective of
     everyday listening
- If hearing aid users: Use Phonak hearing aids that are compatible with the remote microphone ALD and be willing to continue using hearing aid(s) during the trial.
- If non-hearing aid users: Be willing and able to use a receiver device e.g.,
   'Roger Focus' which will be paired to the ALD during the device use periods of the trial. This receiver will be provided by the trial alongside the ALD.

Partners/caregivers/close family members of participants will be asked to complete a caregiver burden questionnaire (SOS-Hear) as part of the trial (non-mandatory). If their participation is declined, a participant's ability to take part will not be affected.

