**Table 1: Outcome Measures** 

Measure	Descriptors	Domain Assessed	
CNC test	Phonemically balanced word list presented in 2 listening situations (quiet & with noise). Phonetically imitated; percentage of correct phonemes (speech sounds) calculated 	Speech perception	
LiSN-S test	A Speech Reception Threshold is established in 4 conditions (vary in vocal differences & location to noise) to provide binaural assessment of speech perception (ability to segregate a target speech signal from background noise in a 3D-auditory environment) 	Spatial processing	
Tolerability, Acceptability & Satisfaction (Appendix 1)	7-point Likert scale designed to investigating perceived usefulness, ease of use and behaviour intention	Tolerability, Acceptability &	
Record of Adverse Events, Undesirable Effects &Technical Issues	Adverse Events, undesirable effects and technical issues will be reported by participants (to the trial team at all follow-ups and on an ad-hoc basis).	Satisfaction	
SUS (Appendix 2)	10-item Likert originally designed to measure perceived ease-of-use of a device or system/technology; also provides usability (8-items) &learnability (2-items) subscales.	Usability	
IOI-HA (Appendix 3)	7-item questionnaire designed to evaluate effectiveness of hearing aid treatments. This will be completed by participants who use hearing-aids.	Hearing-aid satisfaction	
Compliance Diary	Participant reported daily diary of ALD use, including setting (e.g., meeting, transport, telephone) and their perceived experience of ALD use in real-time	Compliance	
Number of participants who withdraw	The number of participants who are randomised but subsequently withdraw from the trial will be recorded. Reason/s for withdrawal and time-point details will be collected.	•	
NMDAS	Semi-quantitative, reproducible clinical rating scale of disease progression designed specifically for all forms of mitochondrial disease 	Disease burden	
SSQ-12 (Short Version) (Appendix 4)	12-item version of full SSQ (a subjective assessment of listening and hearing ability in a variety of situations encountered in everyday life) 	Subjective hearing/ listening ability	
CPIB (Appendix 5)	Verbal communication assessed in a range of interactions (46 items); validated and reliable PROMIS measure 	Communicative participation	

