# TRIAL PROCEDURES

Screening / Confirmation of Eligibility

Formal screening activities will be undertaken once the participant has provided

consent. In advance of this, the research team will review the medical history of

potential participants to confirm that it is worth proceeding with formal screening

activities.

A screening log, which will include details of all participants who are formally screened

will be retained. This log will include the reason for any screen failures (if applicable).

The following assessments/activities will be conducted at the screening visit at

Newcastle University:

Written Informed Consent

• Collection of Medical History, medication details and demographics (to

include age, sex, ethnicity, genetic diagnosis, alcohol consumption, smoking

status, socio-economic status i.e. postcode and employment, activities of daily

living)

Newcastle Mitochondrial Disease Adult Scale (NMDAS)\*

Atkin & Fisher's Articulation Survey\*

• Pure-tone-audiometry (eligibility assessment)

• Speech-in-noise (SiN) tests

\*If an NMDAS has been performed within 6 months prior to the visit, the results from

the existing NMDAS can be used and there will be no requirement to perform this

assessment at the visit.

The following assessments/activities will be conducted at the screening visit at

NE1Hear (see Table 1):

• LiSN-S test (eligibility assessment)

• Eligibility Confirmation

Baseline Visit (Week 0)

It is anticipated that, once eligibility has been confirmed, participants will proceed directly to Baseline (on the same day). However, this is not mandatory. In all circumstances, Baseline should take place within 14 days of confirmation of eligibility.

Baseline Assessments/Activities will consist of:

- Verbal Re-confirmation of Consent (agreement to continue participation).
- Fitting of ALD
- **CNC test\*** (completed in two conditions –ALD-Aided & non-ALD-Aided; test order will be randomly allocated to participants)
- Participant completed questionnaires: SSQ-12, MFIS, CPIB, SPaRQ, LIFE-H (Short Form), WHOQOL-BREF, IOI-HA (if applicable)
- Caregiver completed questionnaire (if applicable): SOS-HEAR.
- Clinical review of medical notes and collection of existing medical information and previous results. Including:
  - Neuroimaging (e.g., MRI)
  - Neurophysiology (e.g., Nerve conduction studies, electromyography, EEG)
  - Cognitive tests
  - Laboratory tests
  - Genetic tests and mtDNA heteroplasmy levels (results from any tissues)

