# **STATISTICS**

Compliance, tolerability, satisfaction, experience and withdrawal data will primarily be summarised using descriptive statistics and/or visually.

Where appropriate, suitable mixed models may be used to explore longitudinal effects on these data (e.g., temporal within subject changes in compliance). The analysis of the secondary trial objectives efficacy outcome data) will be considered exploratory given the trial sample size.

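### The LiSN-S inclusion cut-off, as printed, describes a result in the normal range although it is labelled as impairment

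*Protocol*

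**What the plan says.** All statements are in the Protocol.

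- Inclusion Criteria, parent requirement: participants must "Have evidence of impaired speech perception in background noise due to" one or both of two causes.
- First limb, a sound-detection defect: "pure-tone-audiometry, ≥60 dBHL in the poorer ear) and/or". Here the inequality points towards worse hearing.
- Second limb, measured on the LiSN-S Speech Reception Threshold: "Impaired auditory processing (≤2 SDs from the normative mean". There is no minus sign and no word such as below, beyond or worse.
- A separate hearing requirement applies to everyone: "Have confirmed hearing loss- via NMDAS hearing score of: 2 (mild), 3 (moderate), or 4 (severe").
- Trial Procedures, screening at NE1Hear, lists "LiSN-S test (eligibility assessment"), so the result is used to decide entry.
- Table 1 describes the measure: "A Speech Reception Threshold is established in 4 conditions". It gives neither the scoring direction nor normative values.

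The protocol does not restate or correct the 2 SD cut-off anywhere else.

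**The concern.** The second limb is meant to identify people whose auditory processing is impaired, but a distance of at most 2 SDs from a normative mean is the conventional description of a normal result. The two limbs of one criterion therefore point in opposite directions: the audiometry limb selects the worse results, and the LiSN-S limb, taken literally, selects the unremarkable ones.

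This matters for anyone who does not reach 60 dBHL in the poorer ear, because that person's eligibility rests on the LiSN-S limb alone. If staff apply the text, people with a marked processing deficit are turned away and people without one are admitted. If staff apply the evident intent, each LiSN-S-only participant more than 2 SDs worse than the norm enters against the printed criterion, and the Deviations section requires departures from the protocol to be logged. The Eligibility Criteria section allows the assessment to be delegated to suitably experienced staff who are not audiologists, so the wording should be sufficient by itself. With 12 participants planned, a few such cases would alter who was studied.

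**Working it through.** **No planned figure to reproduce.** The cut-off is an entry threshold. No sample size, power or error rate depends on it, and the Statistics section says that the efficacy analysis "will be considered exploratory given the trial sample size". The check is therefore who meets the limb under each reading.

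**Inputs.** The 2 SD figure and the inequality come from the Inclusion Criteria. Two things are assumed because the protocol does not give them: LiSN-S normative scores are roughly normal, and patient scores are normal with the same SD as the norms (unit SD). Let z be the distance from the normative mean in SDs, signed so that negative means worse. This sign is a convention for the calculation and makes no claim about how the test is scored.

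**Step 1. Individual cases.**

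- At the mean, |z| = 0 ≤ 2, so the printed limb is met.
- At 3 SDs worse, |z| = 3 > 2, so the printed limb is not met.

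**Step 2. What the wording describes in a normative population.**

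- Within 2 SDs: Φ(2) − Φ(−2) = 0.9772 − 0.0228 = 0.9545, or 95.4%.
- Signed reading, z ≤ +2: Φ(2) = 0.9772, or 97.7%. Treating the number as signed therefore does not make it a test of impairment.
- At least 2 SDs worse, z ≤ −2: Φ(−2) = 0.0228, or 2.3%.

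This step shows only that the printed range is the normal range. It does not describe the trial's candidates.

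**Step 3. Candidates who depend on this limb.** For an assumed patient mean m, the share passing is

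- printed rule: Φ(2 − m) − Φ(−2 − m)
- at least 2 SDs worse: Φ(−2 − m)

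| Assumed mean m | Printed rule | At least 2 SDs worse |
|---|---|---|
| −1 | Φ(3) − Φ(−1) = 0.9987 − 0.1587 = 84.0% | Φ(−1) = 15.9% |
| −2 | Φ(4) − Φ(0) = 50.0% | Φ(0) = 50.0% |
| −3 | Φ(5) − Φ(1) = 15.9% | Φ(1) = 84.1% |
| −4 | Φ(6) − Φ(2) = 2.3% | Φ(2) = 97.7% |

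The equal shares at m = −2 do not mean that the rules agree. One accepts z from −2 to +2 and the other accepts z of −2 and below, so they share only the boundary value and pick different people.

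**Step 4. Who is outside the problem.** The limbs are joined by and/or. Anyone at or above 60 dBHL in the poorer ear qualifies whatever the LiSN-S result, and nobody enters without an NMDAS hearing score of 2 to 4.

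**The case against.** Four points can be made for the plan.

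1. *The intent is plain.* The number is a parenthesis to the word impaired, under a parent requirement for impairment, and a careful assessor would not certify someone at the normative mean. This stands as evidence of what was meant. It does not make the printed threshold correct, and a threshold that must be overridden to be applied needs repair.

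2. *A minus sign may have been lost when the PDF was read.* The exclusion criterion on conductive loss appears without a dash between 500 and 3000 Hz, while dashes survive elsewhere, for example in the Background prevalence range. The loss is possible but not shown, so the source file must be checked first. If it has the minus sign, the inversion disappears.

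3. *The reach is limited.* This stands. A reader might infer that the trial would fill with normal listeners, at 95.4% against 2.3%, or about 42 times too many (0.9545 / 0.0228). The documents do not support that. Those percentages describe a normative population, which cannot enrol, because entry needs genetically confirmed mitochondrial disease and an NMDAS hearing score of 2 to 4. Nor would the whole trial study people without the deficit: the audiometry limb is unaffected, and people admitted in error would lack the processing deficit, not hearing loss.

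4. *The scoring details are not in the protocol.* This also stands. A reader might want the rule rewritten as a signed deviation score, a raw threshold in dB or an age-specific norm. The protocol states none of these. It also does not name which of the four LiSN-S conditions is used, but that is detail a test procedure can supply and is not part of this error.

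**Conclusion.** The point holds in a limited form. As printed, the LiSN-S limb contradicts its label and its parent criterion, and no other section corrects it. It is a wording error in an entry threshold and does not show that the sponsor intended to recruit people with normal processing.

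It affects only candidates with a pure-tone average below 60 dBHL in the poorer ear who already meet the NMDAS hearing requirement. The number of such candidates, and how many would be wrongly admitted or refused, cannot be derived from the protocol. The direction and scale of the effect depend on where patients lie: on the assumptions above, the printed rule admits far too many if patients average 1 SD worse than the norm, and far too few if they average 3 or 4 SDs worse. No single multiplier is supported. The conclusion assumes that the source file carries the same text. The contradiction itself needs no distributional assumption; only the percentages do.

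**What to change.** 1. Check the source file of the protocol for a minus sign before the 2.
2. Reconcile the cut-off with its label. Keep the sponsor's own 2 SD figure and state the direction in words, for example: *at least 2 SDs worse than the normative mean*. Words are safer than a bare inequality here because the protocol does not say which way the score runs.
3. Put the same wording on the eligibility CRF.

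The cost is one line in the Inclusion Criteria and one on the CRF, handled through the protocol's Amendments process. Sample size, randomisation, visit schedule and analysis are unchanged.

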#### **Exclusion criteria**

Participants will not be eligible if they:

- Have an NMDAS hearing score of 0 or 1 no communication problems; tinnitus or deterioration from prior 'normal'
- Have an NMDAS speech score of 3 (moderate difficulties) or above
- Have profound/end stage hearing loss i.e. NMDAS hearing score of 5
- Have conductive hearing loss (≥10-dB air-bone gap at 500 3000 Hz)
- Have current local ear intolerances or issues preventing hearing aid/ALD effectiveness or use i.e., ear infection, significant earwax
- Are currently using, or have previously used, a Roger On remote microphone assistive listening device
- If hearing aid users:
  - Use of non-compatible hearing aids (non-Phonak)
  - Planning a change to their hearing aid(s) during the course of the trial
- Any other medical issues, which in the opinion of the investigator would preclude involvement.

**Note on Participant Genotypes** Mitochondrial disease hearing loss is commonly associated with the m.3243A>G pathogenic variant. In order to ensure that this genotype is adequately represented within the study population, a minimum of 50% of participants should be recruited who have the m.3243A>G genotype. A log of participant genotypes will be maintained and the numbers of relevant genotypes monitored. Once a total of six participants with other genotypes have been recruited, recruitment will be restricted to participants with m.3243A>G only.

# RECRUITMENT AND CONSENT

#### Participant identification

Patients will be identified for the trial by their direct clinical care team at the Newcastle Mitochondrial Disease Clinic for Adults and Children. This will be via screening of clinic

lists and by interrogation of the Wellcome Centre for Mitochondrial Research Patient Cohort: A Natural History Study and Patient Registry (MitoCohort) (previously known as the MRC Mitochondrial Disease Cohort), REC Ref: 13/NE/0326.

The MitoCohort, which is a natural history study and patient registry, has > 1900 registered patients with extensive storage of clinical and genetic information. Patients registered on the MitoCohort have consented to receive information about clinical trials and studies for which they may be eligible.

The MitoCohort database will be interrogated for adult patients registered at the Newcastle site with a genetically confirmed diagnosis of mitochondrial disease and mild to severe hearing loss (NMDAS hearing subscale score: 2 to 4).

In addition to recruitment from the MitoCohort, patients seen by the Mitochondrial Clinical Service in Newcastle (at the Newcastle Mitochondrial Disease Clinic for Adults and Children), who are identified by their direct care team as being potentially eligible for the trial, may also be approached.

The trial will also be publicised on a number of websites including the website of mitochondrial disease charities and partner organisations (i.e. the Lily Foundation) and promoted at public and patient engagement events and conferences. Any website or trial advertisement will advise patients who are interested to contact the trial team for further information and a clinical referral to the trial team in Newcastle will be requested.

Potentially eligible patients will be sent an invitation letter along with a copy of the relevant Participant Information Sheet (PIS), or will be contacted (via telephone, email or in person) by their direct clinical care team and invited to participate.

A trial invitation/pre-screening log will be kept which will include details of all individuals who are invited to participate in the trial/are pre-screened for trial participation. This log will include the reason for declining the invitation or pre-screen failure (if applicable/provided).

#### **Informed Consent**

Written informed consent will be obtained from all participants prior to the start of screening assessments. This will be obtained by appropriately qualified, experienced and delegated members of the research team at site.

Consent will be received by means of initialling to confirm agreement of each consent statement followed by participant dated signature and dated signature of the person who received the informed consent.

A copy of the signed Informed Consent Form will be given to the participant and a copy filed in their hospital records. The original signed Consent Form will be stored in the Investigator Site File (ISF).

[figure not shown]
A letter will be sent to the participant's general practitioner to inform them of their patient's participation in this trial. A copy of this letter will be filed in the participant's hospital records.

A caregiver, close family member, or partner, of each participant will be asked to complete a Caregiver Burden Questionnaire (SOS Hear) – this will be optional and a participant will still be able to take part without this. Completion of the questionnaire by the caregiver/family member/partner will be taken as their consent to be involved. Separate written consent will not be obtained.

No identifiable information about the caregiver or family member who completes the questionnaire will be used in the analyses.

Email address and/or mobile phone number of participating caregivers/family members will be collected and stored on REDCAP in order to send out links to online questionnaires (if applicable).

# TRIAL PROCEDURES

Screening / Confirmation of Eligibility

Formal screening activities will be undertaken once the participant has provided

consent. In advance of this, the research team will review the medical history of

potential participants to confirm that it is worth proceeding with formal screening

activities.

A screening log, which will include details of all participants who are formally screened

will be retained. This log will include the reason for any screen failures (if applicable).

The following assessments/activities will be conducted at the screening visit at

Newcastle University:

Written Informed Consent

• Collection of Medical History, medication details and demographics (to

include age, sex, ethnicity, genetic diagnosis, alcohol consumption, smoking

status, socio-economic status i.e. postcode and employment, activities of daily

living)

Newcastle Mitochondrial Disease Adult Scale (NMDAS)\*

Atkin & Fisher's Articulation Survey\*

• Pure-tone-audiometry (eligibility assessment)

• Speech-in-noise (SiN) tests

\*If an NMDAS has been performed within 6 months prior to the visit, the results from

the existing NMDAS can be used and there will be no requirement to perform this

assessment at the visit.

The following assessments/activities will be conducted at the screening visit at

NE1Hear (see Table 1):

• LiSN-S test (eligibility assessment)

• Eligibility Confirmation

Baseline Visit (Week 0)

It is anticipated that, once eligibility has been confirmed, participants will proceed directly to Baseline (on the same day). However, this is not mandatory. In all circumstances, Baseline should take place within 14 days of confirmation of eligibility.

Baseline Assessments/Activities will consist of:

- Verbal Re-confirmation of Consent (agreement to continue participation).
- Fitting of ALD
- **CNC test\*** (completed in two conditions –ALD-Aided & non-ALD-Aided; test order will be randomly allocated to participants)
- Participant completed questionnaires: SSQ-12, MFIS, CPIB, SPaRQ, LIFE-H (Short Form), WHOQOL-BREF, IOI-HA (if applicable)
- Caregiver completed questionnaire (if applicable): SOS-HEAR.
- Clinical review of medical notes and collection of existing medical information and previous results. Including:
  - Neuroimaging (e.g., MRI)
  - Neurophysiology (e.g., Nerve conduction studies, electromyography, EEG)
  - Cognitive tests
  - Laboratory tests
  - Genetic tests and mtDNA heteroplasmy levels (results from any tissues)
  - Other relevant assessments (e.g., audiology, brainstem evoked potential).

